2.6 Analysis^[SP1] of the secondary objectives

A secondary objective of this study is to assess the anti-tumor activity of LDK378 in fasting and fed states. The primary evaluation of the anti-tumor activity of LDK378 will be based on investigator assessment of response (Overall Response Rate, Progression-Free Survival, and Duration of Response) using the FAS per RECIST 1.1 for patients with neuroblastoma and other solid tumors, and IWG criteria for patients with lymphoma. In patients with neuroblastoma, disease assessable at screening only by MIBG scans and by bone marrow evaluation will be treated as non-target lesions. MIBG response will be listed.

Overall Response rate

ORR is defined as the proportion of patients with a best overall response (BOR) of complete response (CR) or partial response (PR) for RECIST. For CHESON: The evaluation of overall disease response at each assessment is a composite of the individual radiological responses (index and non-index lesions, new lesions), laboratory test (bone marrow) and clinical responses (lymphoma related clinical symptoms). ORR will be summarized by indication and by treatment group, where the patients are pooled from both the dose escalation and expansion phases for MTD / RDE determined for each regimen, and exact 95% confidence intervals will be presented.

In addition, for the expansion group patients with ALK activated neuroblastoma, a Bayesian approach will be used to estimate the ORR based on RECIST 1.1 data, along with a 95% credible intervals based on the posterior distributions, using minimally informative unimodal Beta prior distributions. The prior clinical assumption for LDK378 in this selected patient population will be used in order to derive a minimally informative unimodal Beta prior distribution that reflects the level of uncertainty around the ORR before starting the current trial. At completion of the study, this prior distribution will be updated with all data available from the expansion group patients with ALK activated neuroblastoma (including those treated at the MTD in the dose escalation part) in the FAS. Once updated, the posterior probability that the true ORR at the MTD/RDE for these patients lies in the following categories will be presented:

- [0, 10%) insufficient antitumor activity.
- [10%, 20%) limited antitumor activity.
- [20%, 30%) moderate antitumor activity.
- [30%, 100%] substantial antitumor activity.

If the observed ORR is equal to or greater than 30%, then this will be considered as preliminary evidence of substantial antitumor activity of LDK378 in ALK activated neuroblastoma. If the observed ORR is between 20% and 30% then this will be considered as evidence of moderate antitumor activity, and as limited antitumor activity if it is between 10% and 20%. If the observed ORR is less than 10% (i.e. ≤ 2 CR or PR out of 25), then insufficient antitumor activity will be declared.

Note that for a sample size of $n = 25$ (see section 10.8), if the observed ORR is greater than or equal to 20% (i.e. ≥ 5 CR or PR), then the true ORR has a posterior risk of less than 10% of being in the insufficient antitumor activity category.

A minimally informative unimodal Beta prior distribution of the true ORR is derived as follows. A priori it is assumed that the true mean of the ORR equals 20%. A true ORR of 20% is the midpoint between limited and moderate antitumor activity and serves as a compromise between a skeptical view assuming the treatment has only limited antitumor activity and an optimistic view assuming the treatment has moderate antitumor activity. The parameters of the minimally informative Beta prior distribution of the ORR are then derived as $a=1/4$ and $b=1$.

Best Overall Response

Best overall response (BOR) is the best response recorded from the start of the treatment until disease progression. Patients with a BOR of 'UNKNOWN' will be treated as non-responders when estimating ORR. If any non-palliative cancer therapy is taken while on study any subsequent assessments will be excluded from the BOR determination. MIBG response score per curie criteria will be recorded and listed for patients with neuroblastoma who had MIBG scan.

Determination of BOR per RECIST 1.1

ORR is defined as the proportion of patients with a best overall complete response (CR) or partial response (PR) per RECIST 1.1.

For patients with the primary diagnosis other than lymphoma, BOR will be based on the overall lesion assessment per RECIST 1.1. The evaluation of overall lesion response at each assessment is a composite of the target lesion response, non-target lesion response and presence of new lesions (for details see Protocol Appendix 5).

The BOR for each patient is determined from the sequence of overall (lesion) responses according to the following rules:

- CR = at least two determinations of CR at least 4 weeks apart before progression
- PR = at least two determinations of PR or better at least 4 weeks apart before progression (and not qualifying for a CR)
- SD = at least one SD assessment (or better) > 29 days after start of treatment (and not qualifying for CR or PR).
- PD = progression ≤ 85 days after start of treatment (and not qualifying for CR, PR or SD).
- UNK = all other cases (i.e. not qualifying for confirmed CR or PR and without SD after more than 29 days or early progression within the first 85 days).

Determination of BOR per IWG criteria

For patients with the primary diagnosis of lymphoma, BOR will be based on the overall lesion assessment and disease response assessment per IWG (Cheson) response criteria. See Section 14.6 of protocol for guideline for efficacy evaluation in lymphoma patients based on IWG (Cheson) response criteria.

The BOR for each patient is determined from the sequence of overall radiological responses and overall disease responses according to the following rules:

- CR = at least one overall disease response of CR
- PR = at least one overall radiological response or overall disease response of PR (and not qualifying for CR)
- SD = at least one SD overall radiological response > 29 days after start of treatment (and not qualifying for CR or PR)
- PD = progression \leq 85 days after start of treatment (and not qualifying for CR, PR or SD).
- UNK = all other cases.

In general, in the determination of BOR, a patient who had a CR cannot subsequently have a lower status other than a PD, e.g. PR or SD, as this would imply a progression based on one or more lesions reappearing, in which case the status would become a PD.

Once an overall lesion response of PR is observed this assignment must stay the same or improve over time until progression sets in, with the exception of an UNK status.

If there are no baseline scans available at all, then the overall lesion response at each assessment should be considered Unknown (UNK).

Duration of response

Among patients with a confirmed PR or CR per RECIST 1.1 or with a response (CR or PR) per IWG criteria, DOR is defined as the time from first documented response (PR or CR) to the date of first documented disease progression (PD) or death due to any cause.

DOR will be described separately by indication and by treatment group, and by expansion group in tabular and graphical format for patients treated at MTD/RDE by expansion group, using Kaplan-Meier methods including estimated median (in months) with 95% CI, 25th and 75th percentiles ([Brookmeyer and Crowley 1982](#), [Klein and Moeschberger 1997](#) and Kaplan-Meier estimated probabilities with corresponding 95% CIs ([Kalbfleisch and Prentice 1980](#)) at several time points (including at least 2, 4, 6, 8, 10, 14 months).

2.7 Analysis of other secondary efficacy objectives

Progression-free survival

PFS is defined as the time from the start date of study drug to the date of the first radiologically documented PD or death due to any cause per RECIST 1.1, for patients with solid tumor; and from the start date of study drug to the date of the first PD as overall disease response or death due to any cause per Cheson, for patients with lymphoma.

If a patient has not progressed or is not known to have died at the date of analysis cut-off or has received any further anticancer therapy, PFS will be censored at the date of the last adequate tumor evaluation before the cut-off date or before the start of the new anticancer therapy date, whichever is earlier. Clinical deterioration will not be considered as a qualifying event for progression.

In particular, PFS will be censored at the last adequate tumor assessment if one of the following occurs:

- 1: Ongoing without event
- 2: Lost to follow-up

- 3: Withdrew consent
- 4: Adequate assessment no longer available
- 5: Initiation of new cancer therapy prior to progression
- 6: Event after ≥ 2 missing tumor assessments

PFS will be described in tabular and graphical format for patients treated at MTD/RDE by expansion (disease) group, and also by indication and by treatment group using Kaplan-Meier methods as described for DOR, including estimated median (in months) with 95% CI, 25th and 75th percentiles and Kaplan-Meier estimated probabilities with corresponding 95% CIs at several time points (including at least 2, 4, 6, 8, 10, 14 months). Censoring reasons will also be summarized. Also duration between treatment start date and cut-off date, and PFS follow-up time will be summarized by expansion, and also by indication and by treatment group.

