#### **7.1.4 Follow-up period**

All patients will have a Study Evaluation Completion (SEC) visit 30-days (up to 37 days) after the last dose of LDK378. At this time AE, SAE and concomitant medication (including subsequent antineoplastic therapy) information during the follow-up period will be recorded on the AE eCRF and Novartis will be informed as necessary.

Patients lost to follow-up should have this documented on the appropriate eCRF and attempts made to contact the patient to ascertain the reason and required study information, as described in [Section 7.1.3](#).

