### **7.2 Assessment types**

#### **7.2.1 Efficacy**

Disease will be assessed as per RECIST v1.1 ([Appendix 5](#)) in patients with solid tumors, and per IWG criteria ([Appendix 6](#)) for patients with lymphoma. In addition, patients with neuroblastoma will be assessed by MIBG scanning and bone marrow bilateral aspirate and biopsy at screening. Disease response and progression will be determined by the local investigator. When the revised International Neuroblastoma Response Criteria (INRC) currently in development are final they will be incorporated into this protocol.

At screening (within 28 days of the start of LDK378), all patients will undergo CT with i.v. contrast or MRI of the brain, chest, abdomen and pelvis. If there is clinical evidence of disease in the neck, a CT or MRI of the neck will also be performed. If a patient is intolerant of iodine-based contrast agents, CTs may be performed without contrast or MRI may be used. Visible skin lesions and easily palpable subcutaneous tumors may be measured by physical examination using a ruler or calipers. Ultrasound should not be used to measure sites of disease. Patients with neuroblastoma will undergo MIBG scanning, and bone marrow bilateral aspirate and biopsy at screening. Patients with lymphoma will undergo bone marrow bilateral aspirate and biopsy at screening. MIBG scans should be performed within 28 days of the start of treatment, and bone marrow bilateral aspirates and biopsies should be performed within 42 days of the start of treatment.

Subsequent disease evaluations will be performed on Day 15 ( $\pm 7$  days) of cycles 2, 4 and 6. After cycle 6, disease evaluations will be performed on Day 15 ( $\pm 7$  days) of every 4th cycle (e.g., C10, C14), or sooner if there is clinical evidence of disease progression. Post Cycle 14, disease evaluations will be performed every 6 cycles (e.g., C20, C26, C32, etc.) and also performed at EOT. If the last prior disease evaluation was within 28 days of EOT or objective evidence of progressive disease has already been documented, then evaluations do not need to be repeated at EOT.

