Situations C (C1 and C2): Progression or death after one or more missing assessments: The primary analysis is usually using options (1) for situations C1 and C2, i.e.

- (C1) taking the actual progression or death date, in the case of only one missing assessment.
- (C2) censoring at the date of the last adequate assessment, in the case of two or more consecutive missing assessments.

In the case of two or missing assessments (situation C2), option (3) may be considered jointly with option (1) in situation C1 as sensitivity analysis. A variant of this sensitivity analysis consists of backdating the date of event to the next scheduled assessment as proposed with option (2) in situations C1 and C2.

**Situation E: Treatment discontinuation due to ‘Disease progression’ without documented progression:** By default, option (1) is used for situation E as patients without documented PD should be followed for progression after discontinuation of treatment. However, option (2) may be used as sensitivity analysis. If progression is claimed based on clinical deterioration instead of tumor assessment by e.g. CT-scan, option (2) may be used for indications with high early progression rate or difficulties to assess the tumor due to clinical deterioration.

**Situation F: New cancer therapy given:** the handling of this situation must be specified in detail in the protocol. However, option (1), i.e. censoring at last adequate assessment may be used as a default in this case.

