5.4.1 Implementation of RECIST and Cheson guidelines

Disease progression

PD should only be assigned if it is confirmed by an objective assessment method. If a new lesion is detected using an objective assessment method other than radiologic scan, it should be entered on the 'New lesion' RECIST and Cheson eCRF with appropriate method (or method='Other').

In particular, discontinuation due to disease progression or death due to progressive disease, without supporting objective evidence (as defined above), will not be considered as PD in the determination of BOR, the derivation of any efficacy endpoint or efficacy analysis.

Change in imaging modality per RECIST 1.1

Per RECIST 1.1, a change in methodology can be defined as either a change in contrast use (e.g. keeping the same technique, like CT, but switching from with to without contrast use or vice-versa, regardless of the justification for the change) or a change in technique (e.g. from CT to MRI, or vice-versa), or a change in any other imaging modality. A change in methodology will result by default in a UNK overall lesion response assessment. However, another response assessment than the Novartis calculated UNK response may be accepted from the investigator or the central blinded reviewer if a definitive response assessment can be justified, based on the available information.

Change in imaging modality per Cheson

A change in methodology can be defined as either a change in contrast use (e.g. keeping the same technique, like CT, but switching from with to without contrast use or vice-versa, regardless of the justification for the change) or a change in technique (e.g. from CT to MRI, or vice-versa), or a change in any other imaging modality. A change in methodology will result by default in an "Unknown" overall radiological response assessment. However, another overall radiological response than the Novartis calculated "Unknown" response might be accepted from the investigator or the central blinded reviewer if a definitive overall radiological response can be justified to be based on the available information.

Determination of missing adequate tumor assessments

For the computation of ORR, patients without any radiological assessment after the start date of study drug will be counted as failure.

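### PFS and DOR ignore clinical progression by a default that presumes tumour follow-up after treatment; none is scheduled after the EOT visit, so some progressing patients are censored and no sensitivity analysis shows the effect

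*SAP*

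**What the plan says.** For solid tumours, SAP 2.7 ends PFS at "the date of the first radiologically documented PD or death due to any cause per RECIST 1.1". For lymphoma it runs "to the date of the first PD as overall disease response or death due to any cause per Cheson". The section adds: "Clinical deterioration will not be considered as a qualifying event for progression". SAP 5.4.1 applies the same standard to all efficacy endpoints, DOR included: a stop attributed to progression is not PD unless objective evidence supports it.

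This is option (1) for situation E in Table 3-2 of Protocol Appendix 5. Section 3.2.9 of that appendix gives the reason: "By default, option (1) is used for situation E as patients without documented PD should be followed for progression after discontinuation of treatment". Its section 3.2.1 asks a study that does not follow patients for progression after treatment to say so clearly in the protocol, and names phase I and II studies as examples.

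After the last dose the protocol schedules two contacts. The EOT visit (7.1.3, 7.2.1) includes imaging of all tumour sites, waived when objective PD is already on record or when the following holds: "If the last prior disease evaluation was within 28 days of EOT". Then comes 7.1.4: "All patients will have a Study Evaluation Completion (SEC) visit 30-days (up to 37 days) after the last dose of LDK378". That contact collects adverse events and medication, including later anticancer therapy, and no imaging.

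**The concern.** The default is harmless when a patient who stops for clinical progression is scanned until PD is documented, because the event then arrives a little late. Here scanning ends at EOT. A patient who leaves that visit without objective PD is censored at the last adequate assessment because the disease appears to be advancing. Such censoring is informative, and it tends to raise the Kaplan-Meier curve.

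PFS and DOR are secondary endpoints in a study without a control arm, so no comparison cancels the bias. Appendix 5 (3.2.9) calls for one or more sensitivity analyses to be specified. It offers option (2), which counts the clinical progression as an event, for that purpose and for settings where early progression is common or deterioration makes tumour assessment difficult. The SAP plans none.

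**Working it through.** The plan gives no PFS figure to reproduce: there is no target, event count or power for PFS. The check has three parts.

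**1. Premise against schedule.** Appendix 5, 3.2.9 assumes follow-up for progression after treatment. Protocol 7.1.3, 7.1.4 and 7.2.1 schedule nothing tumour-related after EOT, and I found no statement that it is omitted. The premise is not met beyond the EOT visit.

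**2. Who is exempt from the EOT scan.** With scans I days apart, EOT a lag of L days after stopping, and stopping spread evenly (assumed), the waived share is (28 − L)/I. The visit schedule gives scans on Days 36, 78, 120, 204, 288, 414 and so on, so I is 42, then 84, then 126.

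| EOT lag L | I = 42 | I = 84 | I = 126 |
|---|---|---|---|
| 7 days (Protocol 2.6) | 21/42 = 50% | 25% | 17% |
| 14 days (Protocol 7.1.3) | 14/42 = 33% | 17% | 11% |
| 21 days (7.1.3, upper limit) | 7/42 = 17% | 8% | 6% |

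Under the 14-day rule about two thirds or more of these stops still require a scan. The protocol contradicts itself on the lag, and the lag changes who is exempt.

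**3. Illustrative size.** All rates here are assumed; none is in the documents. Progression times are exponential with median 60 or 90 days, and 20% or 40% of progressions are clinical only. The other patients have their event at the next scheduled scan. I compare three treatments of a clinical-only progressor, reading the Kaplan-Meier curve at 4 × 30.4375 = 121.75 days:

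- event at progression (option 2);
- SAP rule with EOT at 14 days and the 28-day waiver, the baseline scan counting toward it. A required EOT scan shows PD in 80% or 50%; everyone else is censored at the previous scan;
- every such patient censored at the previous scan, with no EOT scan.

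The first column below can be checked by hand, because almost all progression up to Day 120 has been counted by then: 2^(−120/60) = 25.0% and 2^(−120/90) = 39.7%.

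| Median | Clinical-only | Option 2 | SAP rule, 80% / 50% | Excess, points | All censored | Excess, points |
|---|---|---|---|---|---|---|
| 60 d | 20% | 24.9% | 28.8% / 29.8% | 3.9 / 4.8 | 31.5% | 6.5 |
| 60 d | 40% | 24.9% | 33.2% / 35.6% | 8.3 / 10.7 | 40.4% | 15.5 |
| 90 d | 20% | 39.6% | 43.7% / 44.8% | 4.1 / 5.2 | 46.7% | 7.1 |
| 90 d | 40% | 39.6% | 48.2% / 50.8% | 8.7 / 11.2 | 55.6% | 16.0 |

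(Differences are taken before rounding.) With the EOT scan the excess is 3.9 to 11.2, about 4 to 11 points. If the baseline scan does not count toward the waiver it is 3.2 to 10.1. With EOT at 7 days it is 4.4 to 12.3, and at 21 days 3.3 to 10.1. The last column, about 7 to 16 points, is an upper bound because it ignores the EOT scan. The model leaves out deaths and new therapy.

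**The case against.** The plan has real backstops. The EOT scan is mandatory outside the waiver, and PD on it is an event. Death from any cause is a PFS event. After cycle 6, Protocol 7.2.1 brings the scan forward when there is clinical evidence of progression. The EOT physical examination covers tumour lesions and has no 28-day waiver. Option (1) is the guideline's own default, and option (2) is permitted, not required. Appendix 5, 4.5.6 foresees patients not followed after treatment and gives them a censoring reason, which the SAP carries and will summarise, along with reasons for stopping treatment. PFS is descriptive, with no test or decision rule.

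Most of this stands, and it rules out two stronger readings. A reader might infer that clinically progressing patients are censored as a class, which gives the 7 to 16 points. The documents do not support that, because most such stops still require an EOT scan.

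A reader might also infer, from the phrase "the date of the first radiologically documented PD or death due to any cause per RECIST 1.1", that marrow progression in neuroblastoma or a caliper-measured lesion is PD for best response but not for PFS. SAP 5.4.1 says "PD should only be assigned if it is confirmed by an objective assessment method", and SAP 5.4 makes those rules govern both 2.6 and 2.7, so this is a wording conflict and not a second source of bias.

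The objection does not remove the remaining group. The waiver has no exception for a stop due to clinical progression, an unevaluable scan is not an adequate assessment, and a death after two or more missing assessments is censored. The summary of censoring reasons does not identify these patients as progressors.

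**Conclusion.** The point holds in a limited form. The rule rests on follow-up that this protocol does not schedule after EOT, the protocol does not say so, and the sensitivity analysis that its own guideline offers is not planned. Some clinically progressing patients are censored as they progress, which tends to overstate PFS and DOR. The excess of about 4 to 11 points in 4-month PFS is an illustration. It rests on the assumed share of clinical-only progression, the assumed median, EOT at 14 days and the assumed yield of the EOT scan. The direction is more certain than the size. DOR follows the same rule, but its size was not computed. The MTD/RDE determination and the ORR activity rule are not touched. This is a cheap improvement to a secondary, descriptive analysis.

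**What to change.** - Keep the primary PFS and DOR rule.
- Add to SAP 2.6 and 2.7 a sensitivity analysis of DOR and PFS under Table 3-2, situation E, option (2): discontinuation for disease progression without documented PD is an event at the discontinuation date. Name that date explicitly, since Table 3-2 uses the visit at which clinical progression was determined and Appendix 5, 3.2.7 uses the EOT visit.
- Report the number of such patients by expansion group.
- State in the protocol or SAP that no tumour follow-up is scheduled after EOT.
- Wording only: in SAP 2.7, replace the radiological condition with objectively documented PD by any method accepted in 5.4.1.
- The sponsor should reconcile the EOT timing: within 7 days of the last dose in Protocol 2.6, against 14 and up to 21 days in 7.1.3.

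The cost is SAP text and one repeat Kaplan-Meier run; the EOT reason and date are already collected. The downside is that the sensitivity estimate will be less favourable and uses a softer, investigator-judged event.
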